2.5.2 Biomarkers of Drug Effect

Although we do not yet know which JAK1 targets must be modulated in order for long term anti-tumor responses to be seen to the BRAF/MEK/JAK1 inhibitor combination, preliminary studies from our group

and others suggests that the RNF125-JAK1-AXL/EGFR and EGFR-SRC family kinase-STAT3 pathways may be critical for the short-term adaptive responses to BRAF inhibition and that prolonged inhibition of the Raf/MEK/ERK/CDK4/Cyclin D1 pathway is required for durable anti-tumor response. Thus, levels of JAK1 protein, downstream targets such as STAT1 and STAT3 and other proteins involved in adaptive signaling responses (EGFR, PDGR, MITF, NF- κ B) will be measured via immunohistochemistry, immunofluorescence or immunoblots from FNAs taken from accessible melanoma lesions before therapy initiation and following BRAF/MEK/JAK1 inhibitor treatment. The preferred time point for on-treatment biopsies is Cycle 1 Day 7 (\pm 3 days). Biopsies may be also taken at any time, including at the time of clinically meaningful events such as response, disease progression or adverse events of interest.

Additionally, biopsy specimens will be evaluated by Reverse Phase Protein Array (RPPA) at RPPA Core Facility, [name] Anderson Cancer Center (Texas, USA). Primary targets of interest for analysis of INCB039110 effect on relevant JAK1 target proteins in tumor biopsy tissue will be evaluated. Frozen biopsy specimens obtained during collection will be sent for analysis of relevant proteins, protein post-translational modifications (phosphorylation and other modifications) and effects on relevant signaling pathways.

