3.1 Eligibility Criteria

3.1.1 *For Dose-Escalation Phase:* Patients must have histologically confirmed, BRAF-mutant (V600E/K) malignancy (molecularly confirmed using Cobas assay or a comparable FDA-approved assay (for exceptions, see below*) that is metastatic or unresectable, have received and tolerated prior BRAF or BRAF and MEK inhibitor (BRAF targeted) therapy or not previously received BRAF targeted therapy, and for which standard curative or palliative measures do not exist or are no longer effective.

- *If test at CLIA-certified lab used a non-FDA approved method, information about the assay must be provided to the Overall Principal Investigator (PI) for approval. (FDA approved tests for BRAF V600 mutations in melanoma include: THxID BRAF Detection Kit and Cobas 4800 BRAF V600 Mutation Test).

3.1.2 *For Dose-Expansion Phase:* Patients must have histologically confirmed, BRAF-mutant (V600E/K) melanoma (molecularly confirmed using Cobas assay or a comparable FDA-approved assay (for exceptions, see below*) that is metastatic or unresectable, have received and tolerated prior BRAF or BRAF and MEK inhibitor (BRAF targeted) therapy at full dose or not previously received BRAF targeted therapy.

- *If test at CLIA-certified lab used a non-FDA approved method, information about the assay must be provided to the Overall Principal Investigator (PI) for approval. (FDA approved tests for BRAF V600 mutations in melanoma include: THxID BRAF Detection Kit and Cobas 4800 BRAF V600 Mutation Test).

3.1.3 Patients must have measurable disease by RECIST, defined as at least one lesion that can be accurately measured in at least one dimension (longest diameter to be recorded for non-nodal lesions and short axis for nodal lesions) as ≥ 20 mm with conventional techniques or as ≥ 10 mm with spiral CT scan, MRI, or calipers by clinical exam. See Section 11 for the evaluation of measurable disease.

3.1.4 Patients may have received any number of prior lines of therapy. All prior systemic anti-cancer treatment-related toxicities must be less than or equal to Grade 1 according to the Common Terminology Criteria for Adverse Events version 4 (CTCAE version 4.0; NCI, 2009) at the time of enrollment. This does not include alopecia and Grade 1 or less peripheral neuropathy.

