3.2 Exclusion Criteria

3.2.1 Patients who received prior systemic anti-cancer therapy (chemotherapy with delayed toxicity, extensive radiotherapy, immunotherapy, biologic therapy, or vaccine therapy) within the last 3 weeks prior to Day 1 of Cycle 1. Patients are permitted to be on dabrafenib and trametinib at start of therapy without wash-out period prior to Day 1 of Cycle 1. Dosing will change to protocol determined dose levels on Day 1 of Cycle 1

3.2.2 Patients must not have received prior JAK1 inhibitor therapy.

3.2.3 Patients who are receiving any other investigational agents. Patients who have taken an investigational drug within 28 days or 5 half-lives (minimum 14 days), whichever is shorter, prior to registration.

3.2.4 Patients with history of RAS mutation-positive tumors are not eligible regardless of interval from the current study. Prospective RAS testing is not required. However, if the results of previous RAS testing are known, they must be used in assessing eligibility.

3.2.5 Patients must have no clinical evidence of leptomeningeal or brain metastasis causing spinal cord compression that are symptomatic, untreated, not stable for \geq 4 weeks prior to Day 1 of Cycle 1 (must be documented by imaging), or requiring corticosteroids to manage metastasis-related symptoms. Subjects who have been off of corticosteroids for at least 2 weeks prior to Day 1 of Cycle 1 or are on a stable dose of \leq 10 mg per day of a prednisone equivalent for >1 month prior to Day 1 of Cycle 1 can be enrolled. Subjects must also be off of enzyme-inducing anticonvulsants for >4 weeks prior to Day 1 of Cycle 1.

3.2.6 History of known immediate or delayed hypersensitivity reactions attributed to compounds of similar chemical or biologic composition to INCB039110, dabrafenib, or trametinib, or excipients or to dimethyl sulfoxide (DMSO).

3.2.7 Uncontrolled intercurrent illness including, but not limited to, ongoing or active serious infection, symptomatic congestive heart failure, unstable angina pectoris, cardiac arrhythmia, uncontrolled diabetes, or psychiatric illness/social situations that would limit compliance with study requirements.

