Optional tumor biopsies will be performed pretreatment, one week (+/- 3 days) after commencing therapy with the combination as part of the phase I dose escalation and dose expansion cohorts, and post-treatment following completion of all study therapy. Biopsies may be also taken at any time, including at the time of clinically meaningful events such as response, disease progression or adverse events of interest. Only lesions that are deemed biopsiable through minimal risk procedures will be selected. For each biopsy, if possible, four core biopsy passes will be made. The first and third cores of tissue will be placed in formalin and then fixed in paraffin. The second and fourth cores of tissue will be flash frozen in liquid nitrogen and embedded in OCT. The first core will be used for IHC and primary outcome assessment. The second core will be used for gene and protein expression analysis. The third and fourth cores will be used to augment testing of cores 1 and 2, should the first and/or second cores be exhausted, and will be stored for future analysis.

Handling of Specimens

As described above, four cores will be obtained and fixed. The SOP for collection, handling, and processing is attached (Appendix H). Samples will either be stored at the individual DF/HCC sites and sent in batch at the time of planned correlative study analysis or sent to and stored at the [name] Laboratory at MGH. FFPE samples will be stored at room temperature. Frozen samples will be stored in a -80 degree freezer.

Shipping of Specimens

Samples may be sent at the time of collection or in batches via overnight shipping. Frozen samples should be sent on dry ice; paraffin blocks may be sent at room temperature conditions. One flash frozen sample will be sent on dry ice to [name] laboratory and the remainder of samples sent to [name] laboratory.

The addresses of the laboratories are:

Massachusetts General Hospital

Jackson 9
 [name]
 [name]

Site Performing Correlative Study: Being conducted only at Massachusetts General Hospital

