10. STUDY CALENDAR

Baseline evaluations are to be conducted within 2-week prior to start of protocol therapy with the exception of scans and x-rays. Scans and x-rays must be done \leq 4 weeks prior to the start of therapy.

Assessments must be performed prior to administration of any study agent. Study assessments and agents should be administered within \pm 3 days of the protocol-specified date, unless otherwise noted.

Procedure	Pre-Study	Cycle 1			Cycles 2+	End of Txt Visit	30 Day F-U Encounter ³	2-6 Month F-U
	Baseline ¹	Day 1 ^{2,b}	Day 8 ⁴	Day 15 ⁵	Day 1 ²			
Dabrafenib and Trametinib ^A		DT ----- DT						
INCB039110 ^B		I-----I						
Informed Consent ^a	X							
Demographic	X							
Medical History	X	X	X	X	X			
Concurrent Medication	X	X	X	X	X			
Serum pregnancy test (B-Hcg)	X ^c	X ^c						
Physical Examination	X	X		X	X	X		
Vital Signs (BP ^d , HR, body temperature)	X ^d	X ^d	X ^d	X ^d	X ^d	X ^d		
ECOG Performance Status	X	X	X	X	X	X		
Dermatology Examination ^e	X				X			X ^e
Height	X							
Weight	X	X			X	X		
Ophthalmology Examination ^f	X				X			
12 Lead EKG	X	X			X			
Hematology/Clinical Chemistry ^g	X	X	X	X	X ^h	X		
Coagulation ⁱ	X							
Tumor Measurements ^j	X ^j				X ^j			
PK Analysis ^k					X ^k			
Optional Tumor Biopsies ^l	X ^l		X ^l			X ^l		
Blood BRAF testing ^m		X		X	X	X		
Rash Prophylaxis ⁿ		X ⁿ		X ⁿ	X ⁿ			
AE assessment ^o	X	X	X	X	X	X	X	
Long term Follow up ^p								X ^p

Color Photography ^q	X ^q				X ^q			
Loperamide ^r	X ^r							

- A. Dabrafenib and Trametinib: doses as assigned; Dabrafenib BID and Trametinib QD.
- B. INCB039110: dosing as assigned per dose level.
- 1. All Pre-study assessments must be completed within 14 days prior to first dose, except for Scans that must be done within 28 days prior to first dose.
- 2. Assessment throughout the study is calendar based starting from first day of dosing (Day 1) in the first cycle of treatment. Dose interruptions should not alter the assessment schedule for any subsequent treatment cycle. Assessment for each visit can be done within 3 days of the projected visit date.
- 3. Follow up encounter, which can be carried out over the phone, should be 30 days from last dose of study drugs (\pm 3 days).
- 4. Medical History, Concurrent Medications, Vital Signs, ECOG Status, Hematology and Blood Chemistry panels will be completed prior to Day 8 treatment.

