 - j. Tumor measurements and radiological exam done every 8 weeks within 7 days of day 1 treatment. Documentation (radiologic) must be provided for patients removed from the study for progressive disease. Brain CT/MRI is required at baseline for patients with melanoma.
 - k. PK samples will be collected pre-dose on Day 1 of Cycles 2, 4 and 6. Also, per Section 6.1.14, for events of visual changes regardless of severity but for which an ophthalmic examination is conducted, a blood sample for PK analysis is encouraged when feasible, and the blood sample should be drawn as close as possible to the time of the event. Also, see section 6.1.16 for PK collection in the setting of Liver Chemistry Changes.
 - l. Optional tumor biopsies will be performed pretreatment. Pre-treatment tissue obtained by biopsy or resection performed according to standard of care may be utilized, provided tissue was obtained within 8 weeks of study entry, and subsequent to the last systemic anticancer therapy received. Optional tumor biopsies will also be performed one week (+/- 3 days) after commencing therapy with the combination as part of the phase I dose escalation and dose expansion cohorts; however, biopsies may be taken at any time, including at the time of clinically meaningful events such as response, disease progression or adverse events of interest. Post-treatment biopsies (following completion of all study therapy) will be optional.

- m. Blood BRAF analysis performed pretreatment C1D1, C1D15, at the beginning of each subsequent cycle and at disease progression (Section 9.1.1).
- n. See table 6.3 for detailed prophylaxis recommended for the first 6 weeks of treatment.
- o. AE assessment starting from the day 1 of dosing throughout the study
- p. After 30 day follow up visit, patient is followed for survival for 2 years. See section 5.6 for full details.
- q. In the case of skin lesions, documentation by color photography, including a ruler to estimate the size of the lesion, is recommended. See section 11.1.3 for full details.
- r. Loperamide should be made available prior to start of study treatment so loperamide administration can begin at the first signs of diarrhea. See table 6-9 for full details.

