We will also utilize highly multiplexed imaging via a high-throughput cyclic immunofluorescence (CycIF) method developed by the [name] lab at DF/HCC to perform deep-profiling at the protein level of single-cells from patient specimens. (Lin *et al.*, 2015) Our collaborator [name] of DF/HCC has optimized this technique - which can permit up to 30 protein markers per slide - for formalin-fixed paraffin embedded patient-tumor specimens (personal communication of unpublished data). We will leverage this approach to validate that proof of mechanism and target engagement of INC039110 by evaluating RNF125-JAK1-AXL/EGFR axis proteins implicated in therapeutic escape including BRAF, CRAF, AKT, JAK1, phospho-AKT, phospho-ERK, phospho-STAT3, EGFR and AXL. We will also use CycIF to immunophenotype tumor-infiltrated lymphocytes and tumor-associated macrophages to characterize the effects of triple JAK1i/BRAFi/MEKi targeting on the immune cell microenvironment. Multi-spectral CycIF images are segmented using freely available tools (ImageJ, CellProfiler) to generate a coordinate map against which fluorescence intensities for all channels can be aligned. Data from 10^5 - 10^7 cells can then be visualized as images and/or studied using dimensionality reduction methods such as principal component analysis or t-Distributed Stochastic Neighbor Embedding.

Furthermore, biopsy specimens will be evaluated by Reverse Phase Protein Array (RPPA) at RPPA Core Facility, [name] Anderson Cancer Center (Texas, USA). Primary targets of interest for

analysis of INCB039110 effect on relevant RNF125-JAK1-AXL/EGFR axis proteins in tumor biopsy tissue will be evaluated. Frozen biopsy specimens obtained during collection will be sent for analysis of protein expression, protein phosphorylation and effects on relevant signaling pathways. 10-15 mg of tumor tissue should be provided for protein extraction and all tumor tissue must be supplied in Precellys tubes with Precellys beads for homogenization. Evaluation will depend upon availability of validated antibodies at MD Anderson Cancer Center. Equivalent biopsy specimens embedded in OCT will be evaluated for tumor and necrotic content.

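### The biopsy analysis claims an INCB039110 effect but does not separate patients already on dabrafenib/trametinib from those who start all three drugs together

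*Combined protocol and SAP*

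**What the plan says.** Section 13.3.1 gives the tissue work an aim specific to INCB039110. For cyclic immunofluorescence it says "We will leverage this approach to validate that proof of mechanism and target engagement of INC039110 by evaluating RNF125-JAK1-AXL/EGFR axis proteins", and the list of proteins that follows includes phospho-ERK, phospho-STAT3, phospho-AKT, EGFR and AXL. For the reverse phase protein array it says "analysis of INCB039110 effect on relevant RNF125-JAK1-AXL/EGFR axis proteins in tumor biopsy tissue will be evaluated".

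The tissue comes from optional biopsies. Section 9.2: "Optional tumor biopsies will be performed pretreatment, one week (+/- 3 days) after commencing therapy with the combination". A post-treatment biopsy and biopsies at other times are also allowed.

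On drug start, the study calendar (Section 10) runs all three drugs from Cycle 1, and its footnote 2 reads "Assessment throughout the study is calendar based starting from first day of dosing (Day 1) in the first cycle of treatment". No lead-in on dabrafenib/trametinib (the doublet) is described.

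Two kinds of patient enter. The expansion criterion in Section 3.1.2 admits those with prior "therapy at full dose or not previously received BRAF targeted therapy", and Section 3.1.1 likewise admits untreated patients to escalation. Section 3.2.1 adds "Patients are permitted to be on dabrafenib and trametinib at start of therapy without wash-out period prior to Day 1 of Cycle 1", and then says that dosing moves to the protocol dose level on that day.

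Footnote l of the calendar lets standard-of-care tissue serve as baseline "provided tissue was obtained within 8 weeks of study entry, and subsequent to the last systemic anticancer therapy received".

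Section 13.3.1 names five immunotherapy agents as prior-therapy factors, to be explored against efficacy outcomes. It gives no biomarker analysis by doublet status at baseline.

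**The concern.** A before/after pair attributes to INCB039110 only what changes because INCB039110 was added. In a patient not on the doublet at baseline, three drugs are added between the two biopsies. The doublet acts directly on one listed marker (phospho-ERK). Section 2.5.2 raises the possibility that it also acts on the others, saying that the RNF125-JAK1-AXL/EGFR and "EGFR-SRC family kinase-STAT3 pathways may be critical for the short-term adaptive responses to BRAF inhibition".

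At stake is the proof-of-mechanism statement. If pairs are not separated, a fall in phospho-ERK could be read as INCB039110 activity when the doublet explains it. An adaptive rise in STAT3 signalling could also hide real JAK1 inhibition. The patients who could answer the question are those already on the doublet. They are neither identified as the analysis set nor helped by footnote l.

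**Working it through.** The plan states no sample size, effect size or test for this endpoint, so there is no figure to reproduce. The check is whether the INCB039110 effect can be identified from the pairs.

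**Step 1. What changes between the two biopsies.**

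| Patient at entry | Added between baseline and about Day 7 | What the pair measures |
|---|---|---|
| Not on the doublet | Dabrafenib + trametinib + INCB039110 | Triple combination |
| On the doublet, dose changed on Day 1 | INCB039110 + a change in doublet dose | Mixture |
| On the doublet, dose unchanged | INCB039110 | Addition of INCB039110 |

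Only the third row matches the claim in Section 13.3.1.

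**Step 2. Phospho-ERK.** Inputs from the documents:
- trametinib 2 mg daily: 62% median inhibition (Section 2.3.1)
- dabrafenib 70 to 200 mg twice daily: 83.9% median inhibition, range 38.0 to 93.3% (Section 2.3.2)

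Both are single-agent figures; no doublet figure is given. Assume that INCB039110 inhibits a further fraction *b* of what remains, with *b* = 0, 20% or 50% (assumed values). For a patient not on the doublet at baseline, with background inhibition *d*:

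observed fall = 1 − (1 − *d*)(1 − *b*)

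| Background *d* | *b* = 0 | *b* = 20% | *b* = 50% |
|---|---|---|---|
| 62% | 62% | 1 − 0.38 × 0.80 = 69.6% | 1 − 0.38 × 0.50 = 81.0% |
| 83.9% | 83.9% | 1 − 0.161 × 0.80 = 87.1% | 1 − 0.161 × 0.50 = 92.0% |
| On an unchanged doublet at both biopsies | 0% | 20% | 50% |

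Against the dabrafenib background, the assumed INCB039110 effect moves the fall by 3.2 to 8.1 percentage points (7.6 to 19.0 against trametinib). The reported between-patient range for dabrafenib alone is 38.0 to 93.3%. A single pair cannot split the two parts. With an on-doublet baseline, the same assumptions give 0% against 20 to 50%, which can be separated in principle.

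**Step 3. Phospho-STAT3.** This is the documents' own JAK1 readout: Section 2.2.1 measures INCB039110 potency in whole blood by IL-6-induced STAT3 phosphorylation. No document gives a doublet effect on it. If the doublet raised it by a fraction *a* and INCB039110 lowered it by *b*, the net change would be (1 + *a*)(1 − *b*) − 1. This is zero when *a* = *b*/(1 − *b*). For *b* = 20% that is a 25% rise; for *b* = 50% it is a 100% rise. Whether rises of that size occur is unknown. The calculation shows only that masking is possible.

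**Step 4. Timing.** Section 2.5.1 puts trametinib steady state at about Day 15, and says dabrafenib Cmax and AUC are about 40% lower on Day 15 than on Day 8. In patients starting the doublet on Day 1, its own contribution is therefore still moving at the one-week biopsy.

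**Step 5. Which baselines are available.** Footnote l attaches its condition to standard-of-care tissue only. The preceding sentence of the footnote, and Section 9.2, offer a study biopsy before treatment without that condition. A patient entering on the doublet can therefore give an on-doublet baseline by fresh biopsy. Standard-of-care tissue taken on the continuing doublet does not, read literally, post-date the last systemic therapy. Footnotes e and f adapt the skin and eye examinations for patients who enter the expansion cohort on the doublet; footnote l has no such adaptation.

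**The case against.** The other side has several good arguments.

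- A reader might infer that no change can ever be ascribed to INCB039110. The documents do not support that. Fresh on-doublet baselines are permitted and isolate the added drug when the doublet dose is unchanged. Dose levels −1 to 3 also hold the doublet fixed while INCB039110 runs from 100 to 400 mg, which allows a weak, non-randomised look at dose response.
- A reader might infer that pooling is planned. It is not stated. Section 13.3.1 describes principal components, gene set enrichment, visualisation and descriptive calculations. The fair criticism is that no separation is specified.
- The 62% and 83.9% figures are single-agent data on the doublet's own pathway marker. They do not show that a fall in phospho-STAT3 could be due to the doublet. For that marker the documents suggest masking, which would give a false null result.
- Section 2.5.2 reports preliminary work and says only that the pathways may be critical.
- The endpoint is exploratory, is absent from the objectives in Section 1.1, and drives no dose decision. Sections 2.5.2 and 13.3.1 already describe parts of the work as effects of the three drugs together.

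These arguments limit the scope and weight of the point. They leave its core standing: the axis-protein claim is worded for INCB039110 alone, pairs from patients not on the doublet measure the triple combination, and the plan does not keep the two kinds of pair apart.

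**Conclusion.** The concern holds in limited form. For patients not on dabrafenib/trametinib at baseline, and for any analysis that mixes them with the others, the pretreatment to one-week change is an effect of the triple combination and does not establish INCB039110 target engagement. Pairs on an unchanged doublet dose can support that claim, but the plan neither requires them nor analyses them separately. Footnote l is a secondary obstacle: it removes one source of on-doublet baseline tissue, not all of it.

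The size cannot be fixed. The share of pairs from patients not on the doublet is unspecified and could lie anywhere from none to all. Biopsies are optional and Section 13.2 caps enrolment at 38 evaluable patients, so usable pairs may be few. The phospho-ERK illustration rests on single-agent figures, a multiplicative model and assumed INCB039110 effects of 0 to 50%; the phospho-STAT3 masking is a possibility with no figure behind it.

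The MTD conclusion is not affected. This is a minor point, worth making because the remedy is cheap.

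**What to change.** **In Section 13.3.1:**
- Base the INCB039110 target-engagement analysis on pairs from patients taking dabrafenib and trametinib at both the pretreatment and the one-week biopsy, with no change in either dose between them.
- Name phospho-STAT3 as the main readout.
- Report pairs from patients not on the doublet at baseline, and pairs with a doublet dose change, separately and as the effect of the triple combination.
- Record doublet status and dose at each biopsy so that pairs can be classified.

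**In footnote l of the study calendar (secondary):** for patients continuing the doublet without wash-out, accept standard-of-care tissue taken on the current doublet within the existing 8-week window, and record the interval from that tissue to Day 1.

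**Cost:** one paragraph of analysis text and one footnote, with no extra biopsies. The downsides are that fewer pairs will support the INCB039110-specific claim, and that older baseline tissue adds elapsed time, and possibly a change in disease state, to the contrast. If too few unchanged-dose pairs are obtained, the result should be described as an effect of the combination only.
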